Please note we will thank NUWAY staff members by citing NUWAY and perhaps individual staff names in the acknowledgments section of academic presentations, posters, and manuscripts that result from these data. We may make periodic presentations to NUWAY staff about study observations and findings throughout the study period and afterward. When appropriate, we will offer CEUs for Social Workers to NUWAY staff for their attendance at these presentations and host inexpensive lunches or coffee hours for NUWAY staff (who are still working from the office during COVID19 at this time). When we are able, we will present NUWAY staff with honoraria as a gesture of thanks for their help with recruitment.

Data capture will also take place using REDCap. We will use REDCap to keep track of our screening procedures and study participation activities.

Measures. Sociodemographic factors will be assessed at the initial baseline measurement (e.g., age, sex, marital status, years of education, race/ethnicity, employment status, and annual household income). A variety of psychometric scales will be used at baseline and throughout the study. Please see Table 2 for the Schedule of Assessments and the text following after Table 2 for more detail about each assessment approach.

Contents of Qualtrics survey and REDCap survey are described herein in full.

Table 2. Schedule of Assessments.

PROTOCOL TITLE: Journaling and Addiction Recovery

VERSION DATE: 13 April 2021

	How long does it take to complete each of these measures	Baseline	At Every PPJ Qualtrics upload	Asked or Tallied after Group Phase Ends (Phase 1)	Asked or Tallied after Independent Practice Phase Ends (Phase 2)	Final Study Activities including 1 Month Follow-up
Baseline characteristics						
Sociodemographics, including current housing situation, i.e., "are you now living in sober living?"	3 minutes	X				
Hospital Anxiety and Depression Scale	3 minutes	X		X	X	X
10-item SIP-AD, addiction consequences	5 minutes	X				
Commitment to Sobriety (full scale)	2 minutes	X		X	X	X
Trait gratitude	2 minutes	X		X	X	X
AA Affiliation Scale	2 minutes	X				
Exposure to trauma	1 minute	X				
Using Medication Assisted Treatment	½ minute	X				
Legal issues: current involvement in civil legal case and current involvement in criminal court case	½ minute	X				
Satisfaction with treatment	2 minutes			X	X	X
Social Desirability Scale	4 minutes	X				

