Open ended questions: Experience with 10 th step, journaling, gratitude practices, and using a planner.	4 minutes	Verbally administered using REDCap			Verbally administered using REDCap	Verbally administered using REDCap
What have you already heard about the study?	1 minute	Verbally administered using REDCap				
Hypothesized Mediators						
Positive and Negative Affect Schedule, including three items comprising the serenity subscale	2 minutes	X	X	X	X	X
Abstinence Self Efficacy Question (single item)	1 minute	X	X	X	X	X
Commitment to Sobriety (single item)	2 minutes		X	X	X	X
Alcohol craving (single item)	½ minute	X	X	X	X	X
Drug craving (single item)	½ minute	X	X	X	X	X
Happiness with Recovery (single item)	½ minute	X	X	X	X	X

PROTOCOL TITLE: Journaling and Addiction Recovery

VERSION DATE: 13 April 2021

Individual items to assess specific impact of PPJ journaling practice ¹ (attached as "single items to assess change")	3 minutes	X	X	X	X	X
Satisfaction with Life	1 minute	X	X	X	X	X
Quality of life scale, modified to compare quality of life during recovery ("now") to quality of life during active addiction ("then") ¹	3 minutes	X	Global quality of life item only	X	X	X
Flourishing scale	2 minutes	X		X	X	X
Treatment Group Only						
# of Qualtrics surveys completed				X	X	X
Ease, helpfulness, satisfaction, effort of PPJ (for control group, ease, helpfulness, satisfaction, effort of filling out the survey questionnaires)	2 minutes		X	X	X	
# group sessions attended				X		
# homework assignments completed				X		
# journal entries completed				X	X	
Count of # of items entered into PPJ		X	X	X	X	
Eligibility rate and consent rate (treatment and control group)						X
On approximately the fourth session of group (halfway through the total # of sessions) ask: "what is working for me in this journaling group is...." And "what is not working for me in this journaling group is...."						
Open Ended Survey Question						
Treatment group: What are your thoughts about Positive Peer Journaling (PPJ) so far?	2 minutes			X	X	
Outcomes						
Recurrence of Substance Use				X	X	X
Treatment Retention at NUWAY (successfully exiting treatment with staff approval versus against staff advice or at staff request)				X	X	X
Qualitative Exit Interview	45 minutes					X
1 month follow up interview	25 minutes					X

Baseline characteristics.

- Sociodemographics

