Exposure to trauma. Participants who have experienced addiction have high rates of exposure to trauma. We will ask about exposure to trauma in order

to describe the sample, that is, to report what percentage of the sample has been exposed to trauma. To determine exposure to trauma, we will use the first question from The Posttraumatic Diagnostic Scale.⁴³ The first question of this instrument asks if the participant has ever experienced life threatening illness, physical assault, sexual assault, military combat, child abuse, accident, natural disaster, or other trauma. Participants will be informed that we will be asking about this in the informed consent document. Please note, we will not assess for symptoms or effects of trauma since our objective is to use the single item to describe the sample. NUWAY regularly screens all residents for trauma. However, if any participant has difficulty with study activities because of trauma or any other reason, we will inform NUWAY. If participants experience distress related to this trauma question or any other element of the baseline questionnaire or screening interview, we will refer them to NUWAY staff.

- Legal involvement. Participants with severe addiction histories such as those in our study have greater rates of involvement with the legal system. Therefore, to better define our population, we will ask, “Are you currently involved in a civil legal case? Are you currently involved in a criminal court case?”
- Medication Assisted Treatment (MAT). Participants with severe addiction histories are often prescribed specific medications to reduce substance use and cravings. Therefore, we will add two items to determine if participants in our sample are using MAT to support their recovery. We ask if they are using MAT and if so, for what substance. For the specific items, see the baseline questionnaire attached to ethos.
- Symptoms of anxiety and depression will be assessed using the Hospital Anxiety and Depression Scale.⁴⁴
- Severity of addiction consequences will be assessed using the 10-item version of the Short Inventory of Problems-Alcohol and Drugs scale (10-item SIP-AD).⁴⁵
- Motivation to remain abstinent will be assessed by the Commitment to Sobriety Scale.⁴⁶
- An individual’s disposition toward gratitude will be assessed with the GQ-6 Gratitude Scale.⁴⁷
- 12 step affiliation will be assessed via the AA affiliation scale⁴⁸

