- Satisfaction with treatment at NUWAY will be assessed via a treatment satisfaction scale.⁴⁹ In previous research, participants who received behavioral activation treatment for substance use disorders had higher treatment satisfaction than individuals in the control group.

- A participant's concern with social approval will be assessed with the Marlow-Crowne Social Desirability Scale.⁵⁰
- We will ask what they already know about this research study (counselors or other clients at the treatment center might have mentioned things about the study). These will be a qualitative open-ended questions.
- Quality of life "now" in recovery compared with "then" in active addiction will be assessed by a modified version of the EUROHIS Quality of Life instrument. ⁵¹

Hypothesized mediators.

- Affect will be assessed with the Positive and Negative Affect Schedule and the Serenity subscale of this instrument.⁵²
- Self-confidence in a participant's ability to abstain from addictive substances will be assessed by the Abstinence Self Efficacy Scale Question: "How confident are you that you will be able to stay clean and sober in the next 90 days, or 3 months?".⁵³
- Commitment to sobriety (single item) "I will do whatever it takes to recover from my addiction."
- Alcohol craving (single item) "Rate the strongest urge to drink you have experienced in the past 7 days"
- Drug craving (single item) "Rate the strongest urge to use drugs you have experienced in the past 7 days"
- Satisfaction with recovery (single item) "In general, I am happy with my recovery"
- Satisfaction in Life will be assessed with the Satisfaction with Life Scale.⁵⁴
- Flourishing will be assessed with Diener's Flourishing Scale.⁵⁵
- We developed several single items to assess change that is directly related to the activities of the journaling practice. These items are uploaded to ethos as "single items to assess change".
- We ask whether the person attended a mutual aid group in the past 24 hours (such as Alcoholics Anonymous).
- It will be important to know whether participants are already doing aspects of the journaling practice. Therefore, at baseline, at the exit interview, and at the 3 month follow up, we will ask participants these questions verbally and we will record answers in REDCap or we will ask these questions in Qualtrics:

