Secondary measures: outcomes and mediators. We will compare rates of treatment retention and recurrence of substance use to the general rates reported by NUWAY. We will also examine pre-post treatment means and standard deviations of hypothesized mediators (affect, satisfaction with recovery, individual items theoretically related to PPJ) to determine if change is in the expected direction. We will also study these constructs to determine if there is reasonable variability in the data we collect or if floor or ceiling effects are present. We may also use single-subject designs⁵⁶ to depict change over time in key constructs by study participant. Qualitative data will be thematically analyzed using the techniques recommended by Braun and Clarke.¹³ Here, the researcher examines transcripts of texts and identifies key themes and how themes relate to one another. These data will inform intervention development and study implementation procedures.

Data analytic techniques to compare treatment and control groups. While this pilot study will not be adequately powered to detect significant effects between treatment and control groups, we will compare differences between the treatment and control groups at baseline and over time using either t-tests or multi-level modeling. T-tests will reveal significant differences between groups and multi-level modeling will show whether rate of change is significantly different between groups.

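### Table 2 gives the single-item commitment mediator and treatment satisfaction no baseline reading of their own

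*Combined protocol and SAP*

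**What the plan says.** Table 2 in Section 5.2 lists "Satisfaction with treatment" among the baseline characteristics. Its baseline cell is empty, and it is first asked after the group phase, then after the independent practice phase and at the final activities. The Measures text also places it under baseline characteristics. The reason given for measuring it is that recipients of behavioral activation in earlier research "had higher treatment satisfaction than individuals in the control group".

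Among the hypothesized mediators, the row "Commitment to Sobriety (single item") is ticked at every survey upload and at all three later points, but not at baseline. A separate row, "Commitment to Sobriety (full scale"), is ticked at baseline and at the three later points. The Measures text describes that instrument under baseline characteristics: "Motivation to remain abstinent will be assessed by the Commitment to Sobriety Scale".

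For analysis, the plan in Section 5.2 states: "We will also examine pre-post treatment means and standard deviations of hypothesized mediators". It also plans to compare the arms at baseline and over time by t-tests or multi-level models. Section 17.3 repeats the comparison of means and slopes, and adds subgroups defined by the baseline level of the factor under study. No baseline-adjusted model is specified. Section 3.2 names commitment to sobriety among the secondary endpoints but does not name treatment satisfaction.

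**The concern.** A measure that is first taken after randomisation has no value untouched by the intervention. For the single commitment item, three planned uses therefore lack an input: the pre-post summary, the comparison of arms at baseline, and the subgroups by baseline level. Its slope can only start after assignment.

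The first upload cannot stand in for a baseline. Section 5.2 puts the baseline battery before randomisation. Under Data Capture, PPJ participants complete a journal entry just before uploading and answer the questionnaires afterwards, whereas controls only fill in the survey. The first reading of the item is thus post-exposure in one arm only.

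The analysis plan also promises to look for floor and ceiling effects. Section 2.2 reports that commitment did not rise in the development study, perhaps because it started at 9.5 out of 10. Without its own baseline, a flat single item cannot be sorted into already high at entry or not moved by PPJ.

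For treatment satisfaction, differences between participants that existed before randomisation stay in the error term, and chance imbalance cannot be checked. Under Section 13.1, people who leave NUWAY in certain ways are withdrawn with only their data to date kept. Anyone withdrawn before the group phase ends has no satisfaction reading at all.

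**Working it through.** The plan gives no figure for either measure. The power statement in Section 17.2 concerns abstinence and retention only. The check is therefore a reading of Table 2 against the analysis plan, followed by an illustration of what a baseline would be worth.

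**Step 1. Schedule in Table 2.**

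| Row | Baseline | Each upload | After Phase 1 | After Phase 2 | Final |
|---|---|---|---|---|---|
| Treatment satisfaction | – | – | X | X | X |
| Commitment, single item | – | X | X | X | X |
| Commitment, full scale | X | – | X | X | X |

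The other mediator rows (affect, self-efficacy, alcohol craving, drug craving, happiness with recovery, the PPJ-specific items, satisfaction with life, quality of life, flourishing) all have a baseline X. The columns line up consistently across these rows.

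**Step 2. Planned analyses against available data.**

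| Analysis | Single item | Full scale | Satisfaction |
|---|---|---|---|
| Pre-post summary | no pre value | possible | not a listed mediator |
| Arms compared at baseline | not possible | possible | not possible |
| Subgroups by baseline level | not possible on its own value | possible | not possible |
| Slope | from first upload, after assignment | from baseline | from end of Phase 1 |
| Arms compared after randomisation | possible | possible | possible |

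**Step 3. Can satisfaction be asked at entry?** Section 9.1 requires about 2 weeks of NUWAY treatment, and the preliminary screen in Section 12.1 requires at least 6 days. On either figure participants have some treatment to rate.

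**Step 4. Value of a baseline covariate.** With correlation r between baseline and follow-up, baseline adjustment multiplies the variance of the arm difference by 1 − r². The documents give no r, so 0.3 to 0.7 is assumed. The detectable difference in SD units (80% power, two-sided 0.05, n per arm) is (1.960 + 0.842) × √(2/n) × √(1 − r²). N = 76 is the figure in Section 17.2. N = 100 is the approximate number to be consented in Section 11.1, so it is an upper limit on the number analysed.

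| r | Variance factor | Reduction | N = 76 (n = 38) | N = 100 (n = 50) |
|---|---|---|---|---|
| 0 (no adjustment) | 1.00 | 0% | 0.643 | 0.560 |
| 0.3 | 0.91 | 9% | 0.613 | 0.535 |
| 0.5 | 0.75 | 25% | 0.557 | 0.485 |
| 0.6 | 0.64 | 36% | 0.514 | 0.448 |
| 0.7 | 0.51 | 49% | 0.459 | 0.400 |

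Each line supposes that everyone has the reading.

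**Step 5. Burden.** Table 2 lists 2 minutes for satisfaction and 2 minutes for the single item: 2 + 2 = 4 minutes. The timed rows with a baseline entry add up to 28 minutes (baseline characteristics and open-ended questions) plus 13.5 minutes (mediators), or 41.5 minutes. The addition is 4/41.5, about 10%.

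**The case against.** The strongest reply is that the construct is already measured. The named secondary endpoint is commitment to sobriety, and the full scale has a baseline and three later readings. Pre-post change, slope, baseline adjustment and baseline-level subgroups can all be done on that multi-item measure, and its baseline can serve as a covariate for the single item. This stands, and it confines the commitment gap to the single item.

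Other replies also carry weight:

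- The bracketed examples in the pre-post sentence name neither commitment nor treatment satisfaction. The sentence does cover hypothesized mediators, however, and the single item is listed as one in both the table and the text.
- A slope does not need a baseline. The surveys run 3–4 times a week in Phase 1 in both arms, so only change before the first survey is missed. If commitment is near its ceiling at entry, as in the development study, that may be little.
- Satisfaction is neither a listed mediator nor a named secondary endpoint, and its stated rationale is a difference between groups. Randomisation supports that comparison without a baseline. A rating after only 6 days of treatment may also predict later satisfaction poorly, which would point to the low end of the range for r.
- No baseline-adjusted model is planned, so the variance reductions are gains available to a changed analysis and not losses in the present one.
- The documents do not show whether the single item is part of the full scale. If it is, its baseline is already being collected and this half of the point becomes a clarification of Table 2.

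These replies limit the size of the point. They do not fill the two empty cells, for which no reason is given.

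**Conclusion.** The point holds as a modest, inexpensive improvement to a pilot whose main aim is feasibility and acceptability. The single-item mediator lacks a pre-randomisation value of its own, so three planned analyses cannot use it as scheduled, and its slopes start after assignment. Treatment satisfaction lacks a baseline for precision and for checking chance imbalance.

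A reader might infer two stronger conclusions, and the documents support neither. The first is that commitment cannot be analysed from baseline; the full scale shows that it can. The second is that the satisfaction comparison is biased; under randomisation with complete data it is not. Nor does the protocol state that PPJ is expected to raise satisfaction. It cites a difference seen in earlier research.

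The precision gain is a 9% to 49% reduction in variance for assumed correlations of 0.3 to 0.7. It applies only among participants who have the reading, so the gain across the trial is smaller if some were enrolled without it. For commitment it is smaller again, because the full-scale baseline is already available as a covariate.

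**What to change.** For participants still to be enrolled, tick the baseline column for both rows in Table 2 and add both measures to the pre-randomisation survey. If the single item appears word for word in the full scale, take its baseline from there for everyone, including those already enrolled, and say so in the table. State in the analysis plan that the baseline values enter as covariates, or as the time-zero reading in the multi-level model.

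For participants already enrolled, use the full-scale baseline as the commitment covariate and compare satisfaction after randomisation only.

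The cost is up to 4 more survey minutes by Table 2's own times and a minor IRB modification. There will be no satisfaction baseline for those already enrolled. If the survey is left unchanged, the least that should be written down is that the full scale is the commitment measure for pre-post and baseline-level analyses, and that satisfaction is compared only after randomisation.

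### The plan does not say which score of the now-versus-then quality-of-life scale is compared between arms, and the t-test has no baseline adjustment; the 'now' score adjusted for baseline should be named

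*Combined protocol and SAP*

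**What the plan says.** The Measures text in 5.2 says: "Quality of life 'now' in recovery compared with 'then' in active addiction will be assessed by a modified version"; the source scale is the EUROHIS. That bullet closes the list that precedes the 'Hypothesized mediators' heading. Table 2 places the same scale under Hypothesized Mediators: "Quality of life scale, modified to compare quality of life during recovery" with quality of life during active addiction. The full scale is scheduled at baseline, after Phase 1, after Phase 2 and at the final activities that include the 1-month follow-up. At each Qualtrics upload the entry is "Global quality of life item only".

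For analysis, 5.2 promises "pre-post treatment means and standard deviations of hypothesized mediators", a check "if floor or ceiling effects are present", and arm comparisons by t-test or multi-level model. Section 17.3 repeats the t-tests and multi-level models and says the pilot is not adequately powered to detect an effect. Neither section says how 'now' and 'then' are combined, which score is compared between arms, whether the baseline 'then' is carried forward, or whether the t-test is adjusted for baseline. The modified items are not in the text available.

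**The concern.** Section 4.1 gives better quality of life in recovery as an aim of PPJ, so this scale bears directly on how the intervention is meant to work. Life in active addiction normally lies before randomization, because 9.1 asks for about two weeks of abstinence at entry (9.3 lets this be waived). PPJ cannot change that period, yet participants re-rate it after treatment.

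If the comparison is scored as one number, two things can happen. Variation in 'then' may add noise to the arm contrast. And if PPJ changes how people remember active addiction, the score can differ between arms with current quality of life unchanged. The second route is conjecture but not empty: only the PPJ arm attends the sessions, and Session 3 in Table 1 includes teaching about how addiction affects positive emotion and stress. As the scoring is left open, the choice could also be made after the data are seen. Under 17.3 the descriptive statistics feed sample-size work for a larger trial, so an undefined score and its SD could carry forward.

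**Working it through.** **The plan's own figures.** Section 17.2 gives power at N=76 for abstinence (.61 and .34) and retention (.94 and .82). With 38 per arm and the arcsine effect size these reproduce as .609, .344, .942 and .815. They have no bearing on quality of life: the documents give no SD, correlation or effect size for it, so everything below is an assumption shown over a range.

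**Inputs.** 38 per arm (N=76 in 17.2) and 50 per arm (about 100 in 11.1), assuming 1:1 allocation and no dropout. True effect 0.5 SD on 'now'; two-sided 5%; t-test power at one post-treatment time point.

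**SD of a difference score.** Let k = SD(then)/SD(now) and ρ = corr(now, then). Then SD(now − then) = SD(now) × √(1 + k² − 2ρk). This exceeds SD(now) only if k > 2ρ, that is, ρ < k/2. With equal SDs the break-even is ρ = 0.5.

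**Power and recall shift, k = 1.** The effective effect is 0.5/√(2 − 2ρ). The last two columns are the chance of a significant result when 'now' has no effect and recalled 'then' alone shifts by s in one arm, an effective difference of s/√(2 − 2ρ).

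| ρ | SD of score | Power, 38 / 50 per arm | s = 0.2, 38 / 50 | s = 0.3, 38 / 50 |
|---|---|---|---|---|
| 0 | 1.414 | 33% / 42% | 9% / 11% | 15% / 18% |
| 0.3 | 1.183 | 44% / 55% | 11% / 13% | 19% / 24% |
| 0.5 | 1.000 | 58% / 70% | 14% / 17% | 25% / 32% |
| 0.7 | 0.775 | 79% / 89% | 20% / 25% | 39% / 48% |

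An unadjusted t-test on 'now' alone has 58% / 70% power and stays at 5% under a recall shift. With k = 0.5 and ρ = 0.3 the difference score has SD √(1 + 0.25 − 0.3) = 0.975, a slight gain. So low correlation costs power, while high correlation restores it but magnifies any recall shift.

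**'Now' adjusted for baseline 'now'.** With an assumed retest correlation of 0.6 the residual SD is √(1 − 0.36) = 0.8 and the effective effect 0.5/0.8 = 0.625. Power is about 77% / 87% (simulation gave about 76% / 86%).

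**Change from baseline, 38 per arm, normal approximation.** Take retest correlation 0.5 for 'now', so its change has SD √(2 × 0.5) = 1 and power 59%.
- If 'then' is recalled identically each time, now-minus-then also has 59%: no loss.
- If 'then' has retest correlation 0.8, its change has SD √0.4 = 0.632. If the two changes are uncorrelated, the score SD is √(1 + 0.4) = 1.183 and power 45%. If they correlate 0.5, it is √(1.4 − 0.632) = 0.876 and power 70%.

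**The case against.** The strongest reply is that the plan never says the two parts are subtracted. If they are separate ratings, 'now' can be analysed alone and both difficulties disappear without touching the instrument. That stands, and is why the point is an unnamed score rather than a faulty test.

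A reader might infer that the scale merely measures sobriety against addiction. For the arm comparison the documents do not support this: 'then' has the same expectation in both randomized arms and, if recalled stably, cancels; it also cancels in change from baseline. The reading applies only to the level of the score within an arm. A reader might also infer that power is lost or the error rate inflated. Neither is established. Loss needs ρ < k/2, power can be equal or higher, and the recall shift is assumed; PPJ itself reviews the past 24 hours and plans the next, without asking anyone to rate life in addiction.

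The comparison also has a rationale. Section 2.1 speaks of an abstinent life more appealing than active addiction, so a relative rating is a defensible thing to collect. Current wellbeing is covered elsewhere without a 'then' anchor: "Satisfaction in Life will be assessed with the Satisfaction with Life Scale", and the Flourishing Scale is listed too. The pilot is declared underpowered, and this is one exploratory measure among many that 3.2 does not name. These points limit the consequence but do not supply the missing definition.

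Finally, it is tempting to drop 'then' from the later surveys. That would remove the only data able to show a recall shift, and would give earlier and later cohorts different surveys in a study already recruiting.

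**Conclusion.** The point holds as a gap in specification. The plan repeats a now-versus-then scale after treatment, calls it a mediator in Table 2, and does not say which score the arms are compared on or adjust the t-test for baseline. The multi-level model of change does use the baseline measurement, but its score is equally undefined.

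Under the assumptions shown (0.5 SD effect, equal SDs, retest correlation 0.6), naming 'now' with baseline adjustment gives about 77% power at 38 per arm and 87% at 50. An unadjusted difference score gives 33-58% and 42-70% for ρ between 0 and 0.5. The adjusted 'now' score also keeps the 5% error rate if recall of 'then' shifts. These figures show what could happen; the documents give no values to show that it does. No primary outcome depends on this measure.

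**What to change.** In the 5.2 Analysis Plan and in 17.3, name the 'now' score as the between-arm quality-of-life mediator, analysed with baseline 'now' as covariate (optionally also baseline 'then'). Keep the later 'then' ratings and report them separately by arm as a recall check. State that any within-person now-versus-then difference describes recovery and is not evidence of a PPJ effect. Reconcile the Measures text, where the scale precedes the mediator heading, with Table 2, where it is a mediator.

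If the items prove to be single comparative ratings, 'now' cannot be extracted. In that case adjust for the baseline comparative score and state that it cannot separate current quality of life from recall of 'then'.

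The cost is analysis-plan wording: no new items, visits or participants, and no survey change. The downside is that the headline score no longer expresses the now-versus-then contrast directly. At a correlation near 0.7 with no recall shift, a difference score could have somewhat more power (79% / 89% unadjusted, against about 77% / 87%).
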